Anatomical variation of femoral nerve location in relation to femoral artery -
An ultrasonographic evaluation

Date: 20th March 2016

Anatomical variation of femoral nerve location in relation to femoral artery - An ultrasonographic evaluation

Introduction:

The femoral nerve block is ideal for surgeries of the femur, knee, or anterior thigh and is often combined with a sciatic nerve block for near complete lower extremity analgesia. The classic teaching is that the femoral nerve lies lateral to femoral artery sandwiched between the fascia iliaca and iliopsoas muscle¹.

Aim:

The objective of the study is to find out the anatomical variation in the site of the femoral nerve in relation to the femoral artery, with respect to the age, sex, and BMI of the patient.

Anatomy:

The femoral nerve is the largest branch of lumbar plexus originating from ventral rami of 2nd, 3rd and 4th lumbar nerves. The nerve descends through the psoas muscle emerging from psoas at lower part of the lateral border. It passes underneath the inguinal ligament lying in the concave groove between iliacus and psoas muscle under fascia iliaca ². At the inguinal crease, it lies 0.5-1 cm lateral to the femoral artery ^{1,3,4}. It divides into anterior and posterior divisions and supplies iliacus, pectineus and muscles of anterior compartment of thigh except tensor fascia lata, and cutaneous innervation to the anterior and medial part of thigh and medial side of the leg. It also supplies articular branches to hip and knee joint.

Sonoanatomy:

The femoral nerve is scanned with high frequency linear probe because of its superficial nature. Distal to the inguinal ligament, it lies lateral to femoral artery deep to fascia iliaca. The artery can be easily identified because of its pulsation and if there is difficulty Doppler can be used. The femoral nerve can be seen as a triangular hyperechoic shadow lateral to the artery². Routinely, distal to the inguinal crease, when the femoral artery bifurcates into the superficial femoral artery and profunda femoris artery, the femoral nerve too divides into an anterior and posterior division. Occasionally, the bifurcation of the artery occurs early, even as high as the inguinal crease ^{5,6}.

Methodology:

200 patients above the age of 18 coming for fixation of fracture femur, will be enrolled in the study after explanation of the details. They will be divided into two groups according to age.

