Group 1 - age between 18 and 60 and Group 2 - age above 60.

Those persons below the age group of 18, patients with any neurological illness that hinders them from giving a valid consent and those with local pathology at the inguinal region will be excluded. Those scans in which measurement is not possible secondary to poor image quality is excluded after enrolment. Those patients in which there is abnormal anatomy of femoral nerve or artery like early division (above the inguinal ligament) also not included in the study.

After explaining the scanning procedure in detail and after ensuring the privacy, inguinal region will be exposed. Scanning will be done by same anaesthesiologist in all the patients. High frequency linear probe of frequency 5-16 Hz of Sonosite X-porte (Fujifilm Sonosite, Inc. Bothell, Wa98021 USA) will be used for scanning and saving image.

The probe is placed on the inguinal crease with pointer facing laterally and the femoral artery is identified by its pulsation. The nerve is identified as a hyper echoic triangular shadow lateral to the femoral artery. If the nerve is not visualised clearly, the probe is adjusted by tilting to get a clear image of the femoral nerve. Once a clear image is obtained, the image will be saved per the patient enrolment number.

A vertical line is drawn from the medial end of the femoral nerve. Another horizontal line is drawn from the 9o'clock position of femoral artery perpendicular to the first line. The distance between the points where the two lines meet and the 9o'clock position of the femoral artery is measured. (fig1)

Fig 1 : measuring horizontal distance

If the femoral artery is branching at the level of inguinal crease, the scanning is done proximally to find out the point where the artery is single. The measurement will be taken at this point.

In addition, the data will be analyzed with respect to the sex, and BMI of the patient to know whether these variables influence the position of the femoral nerve in relation to the femoral artery.

Statistical method:

Pearson Correlation was used to find the correlation between age, BMI and distance between femoral artery & nerve. Independent t-test was used to compare the distance value by age group and gender.

References:

1. Hadzic A (2012) Femoral nerve block. In Hadzic A (ed) Hadzics's peripheral nerve blocks and anatomy for ultrasound guided regional anesthesia , 2nd edn. McGraw-Hill, Newyork, pp 267-279.

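### Does testing age twice, as a continuous variable and as two groups, leave the age conclusion with an inflated error rate?

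*Combined protocol and SAP*

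**What the plan says.** The Aim is to describe how the position of the femoral nerve relative to the artery varies "with respect to the age, sex, and BMI of the patient". Under Methodology, "200 patients above the age of 18 coming for fixation of fracture femur, will be enrolled in the study", and of these patients it says "They will be divided into two groups according to age": "Group 1 - age between 18 and 60 and Group 2 - age above 60".

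The Statistical method section has two sentences. The first is "Pearson Correlation was used to find the correlation between age, BMI and distance between femoral artery & nerve". The second is "Independent t-test was used to compare the distance value by age group and gender". Sex therefore has one analysis (t-test), BMI has one (Pearson), and age has both. The document gives no significance level, no hierarchy among analyses and no rule for reading the two age results together.

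One further sentence in Methodology bears on hierarchy. Sex and BMI are introduced as an addition to what precedes them, "to know whether these variables influence the position of the femoral nerve in relation to the femoral artery". The variables meant there are sex and BMI, not age.

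**The concern.** Two tests of one factor on one outcome, with no stated precedence, give two chances to declare an age effect. A reader could worry that whichever test is significant will be reported as the finding, which would put the real error rate for age above the level quoted for either test.

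The second worry is disagreement. If one age result is significant and the other is not, the plan does not say what would be concluded. Age is the only factor used to form groups, so this touches a central result of the study.

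**Working it through.** The document states no error rate or power, so there is no figure of its own to reproduce.

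**Inputs from the document:** 200 patients; the cut at 60; Pearson on age; independent t-test by age group.

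**Assumed, because not stated:** two-sided 5% per test; all 200 analysed; normally distributed distance; equal-variance t-test; six age distributions with 22% to 78% of patients above 60. A to F give mean/SD in years, with normal components truncated to 18-100.

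**Step 1. No age effect.** The probability that at least one test is significant is

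P(either) = P(Pearson) + P(t-test) − P(both).

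The tests are strongly correlated, so P(both) is far above the 0.05 × 0.05 = 0.25% of unrelated tests. The null columns below use 100,000 replicates per distribution. The columns at r = 0.20 (linear effect) use 20,000.

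| Age distribution | Above 60 | Null: either | Null: both | t-test power, r = 0.20 | Tests differ, r = 0.20 | Median p of the non-significant test |
|---|---|---|---|---|---|---|
| A: 50:50 mix of 35/10 and 75/8 | 49% | 6.8% | 3.1% | 75% | 11% | 0.079 |
| B: 70% 78/8, 30% 40/12 | 71% | 7.1% | 2.9% | 72% | 14% | 0.085 |
| C: uniform 18-95 | 45% | 7.5% | 2.8% | 69% | 17% | 0.093 |
| D: normal 55/18 | 39% | 7.8% | 2.3% | 63% | 23% | 0.108 |
| E: normal 70/13 | 78% | 8.1% | 1.7% | 54% | 32% | 0.128 |
| F: normal 48/15 | 22% | 8.1% | 1.8% | 55% | 31% | 0.134 |

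Each test alone is significant in 4.8 to 5.2%. For A, the formula gives 5 + 5 − 3.1 = 6.9%, against 6.8% simulated.

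**Step 2. Check by another route.** With ρ the correlation between age and the over-60 indicator, P(either) = 1 − P(|Z1| < 1.96, |Z2| < 1.96) for bivariate normal Z. This gives 8.1% at ρ = 0.75, 7.8% at 0.80, 7.3% at 0.866 and 7.0% at 0.90. Two independent tests would give 1 − 0.95² = 9.75%. A separate simulation with other age distributions gave 6.7 to 8.2%, and 8.7% in an extreme case with 89% above 60.

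**Step 3. The rate depends on the reading.** Under no age effect:

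- either test counts: 6.8 to 8.1%
- one test decides: about 5%
- both required: 1.7 to 3.1%

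Only the first exceeds 5%, and the document does not adopt it.

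**Step 4. What disagreement looks like.** At r = 0.20 the tests differ on significance in 11 to 32% of studies; the top of that range comes from the two most unbalanced distributions, E and F. When they differ, the estimates share a sign in 99.2 to 100% of cases.

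**Step 5. What naming one test costs.** At r = 0.20:

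- linear effect: Pearson 81 to 82% power, t-test 54 to 75%
- step at 60: t-test 81 to 82% power, Pearson 54 to 75%

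The loss from a wrong choice is about the same in each direction.

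**Step 6. Scale across the three factors.** Treating the factors as independent, the chance of any false positive with four tests is 1 − (0.932 × 0.95²) = 15.9% to 1 − (0.919 × 0.95²) = 17.1%. With one test per factor it is 1 − 0.95³ = 14.3%. The second age test adds 1.6 to 2.8 points.

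**The case for a change.** The best case for a change is that the omission is real and cheap to fill. The section reads as complete, so the missing hierarchy is not a redaction. With a modest linear effect, between about one study in nine and one in three would yield one significant and one non-significant age result, and nothing says how to conclude. One sentence would settle it before the data are seen, removing no analysis and needing no new data.

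The facts stand and the figures reproduce. The inference that the plan needs changing does not, for three reasons:

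- **The inflated rate belongs to a decision rule that the document does not contain.** The Aim is to describe variation. It states no hypothesis and calls for no yes-or-no verdict on age.
- **The two analyses answer different questions.** Pearson looks for a linear trend over age; the t-test asks whether the mean differs between two predefined groups. Reporting both is ordinary practice, and a reader who sees both estimates is not misled when p-values straddle 0.05.
- **The text is not silent on emphasis.** Age is the only basis for grouping, and sex and BMI enter as additions. That suggests, without stating it, that the age-group comparison is the main one. Against this, the Aim speaks of age rather than age group, and Pearson is listed first. The signal is weak, and it gives no ground for preferring continuous age.

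**Conclusion.** No change is needed. The gap is real but small, and an analyst fills it sensibly by reporting both prespecified age analyses with their estimates. Each is valid alone at about 5%. The 7 to 8% figure arises only if either significant result is counted as an age effect, and it rests on an assumed 5% level and assumed age distributions, since the document gives neither.

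Disagreement between the tests is plausible (11 to 32% at an assumed r of 0.20). It is mostly a matter of results either side of 0.05: the signs agree at least 99% of the time, and the non-significant test has a median p of about 0.08 to 0.13. Naming a main age analysis would be an acceptable optional clarification. The document does not determine which one, and the power lost by a wrong choice is about equal either way.

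### Age, sex and BMI are each tested alone, so if they are associated in this sample the plan cannot say which is independently related to nerve position; one regression should be added.

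*Combined protocol and SAP*

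**What the plan says.** The Aim is to find how the nerve's site relative to the artery varies "with respect to the age, sex, and BMI of the patient". The last paragraph of the Methodology goes further: "In addition, the data will be analyzed with respect to the sex, and BMI of the patient", and the stated purpose is "to know whether these variables influence the position of the femoral nerve in relation to the femoral artery".

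The Statistical method is two sentences. The first is "Pearson Correlation was used to find the correlation between age, BMI and distance between femoral artery & nerve". The second is "Independent t-test was used to compare the distance value by age group and gender". No regression, partial correlation, analysis of covariance, stratified analysis or matching appears anywhere in the document.

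On design, the Methodology states "200 patients above the age of 18 coming for fixation of fracture femur, will be enrolled in the study" and then "They will be divided into two groups according to age". Nothing is said about the mix of sex or BMI within the age groups, or about how many patients fall in each.

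**The concern.** Each planned test answers a marginal question: does mean distance differ between women and men, or does distance rise or fall with BMI? The Methodology's question, whether sex and BMI influence position, is different. In an unrandomised series of femur-fracture patients divided only by age, women may be older than men, or BMI may vary with age. A sex or BMI association could then simply carry an age effect, or a real one could be hidden by it. The same holds in reverse for age, and for any association between sex and BMI.

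What is at stake is the study's conclusion about which patient characteristics go with a shifted nerve. If the three factors are unassociated in the sample, the crude tests are not distorted. The plan as written has no analysis that protects the conclusion if they are associated.

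**Working it through.** The plan has no figure to reproduce: 200 is given without a significance level, power, SD or target effect. The steps below show how far crude tests can drift.

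**Inputs**
- From the documents: 200 patients (Methodology); the nerve 0.5-1 cm lateral to the artery (Anatomy).
- Assumed, because the documents are silent: 100 women and 100 men; within-sex age SD 18 years; age-distance correlation *r* = 0.2 to 0.4; women older by *d* = 0, 5 or 10 years on average; age-BMI correlation ρ = -0.2 or -0.3; two-sided 5% tests.

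**Step 1: sex has no effect of its own.** The overall age SD is √(18² + (d/2)²), which is 18.17 for d = 5 and 18.68 for d = 10. The crude sex difference that age induces is r × d / (age SD), in SDs of distance:
- d = 5: 0.2 × 5/18.17 = 0.055 up to 0.4 × 5/18.17 = 0.110
- d = 10: 0.2 × 10/18.68 = 0.107 up to 0.4 × 10/18.68 = 0.214

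With 100 per sex, the expected test statistic is about difference × √(100/2) = difference × 7.07, so 0.39 to 0.78 and 0.76 to 1.51. The chance of exceeding ±1.96 is then about 7-12% and 12-33%.

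**Step 2: BMI has no effect of its own.** The induced BMI-distance correlation has size r × |ρ|: 0.04 to 0.08 at ρ = -0.2, and 0.06 to 0.12 at ρ = -0.3. On the Fisher scale, multiplied by √197 = 14.04, that is 0.56 to 1.13 and 0.84 to 1.69. The rejection rates are about 9-20% and 13-39%.

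**Step 3: masking.** Suppose the true age-adjusted sex difference is -0.4 SD, opposite to the age effect. The crude difference becomes -0.4 + r × d / (age SD): -0.345 to -0.290 at d = 5, and -0.293 to -0.186 at d = 10.

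**Simulation of steps 1 to 3** (20,000 replicates per cell; within about a percentage point of the approximations above):

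| Scenario | Crude test significant | Model with age, sex, BMI |
|---|---|---|
| No sex effect, d = 0 | 5% | about 5% |
| No sex effect, d = 5 | 7.0-11.7% | about 5% |
| No sex effect, d = 10 | 11.9-32.1% | about 5% |
| No BMI effect, ρ = -0.2 | 8.6-20.5% | about 5% |
| No BMI effect, ρ = -0.3 | 13.4-38.7% | about 5% |
| Sex effect -0.4 SD, d = 0 | 80% | 78.5-86.4% (all d) |
| Sex effect -0.4 SD, d = 5 | 53.4-68.0% | as above |
| Sex effect -0.4 SD, d = 10 | 25.4-53.8% | as above |

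**Step 4: the reverse direction.** If distance depends only on BMI (standardised effect 0.3 to 0.5, assumed), the crude age correlation is significant in 14-29% of studies at |ρ| = 0.2 and in 25-56% at 0.3. If distance depends only on sex (0.5 SD, assumed) and the share of women differs by 20 to 40 percentage points between age groups of 100 each, the age-group t-test is significant in about 10-28%. In a separate simulation of such scenarios (4,000 runs each), the regression flagged age in 4.6-5.3%.

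**Step 5: size in millimetres.** If the 5 mm width of the quoted range spans 4 or 2 SD (assumed), the SD is 1.25 or 2.5 mm. The induced sex difference in step 1 then runs from 0.055 × 1.25 = 0.07 mm to 0.214 × 2.5 = 0.54 mm.

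**Step 6: precision cost of adjusting.** With one other correlated predictor, the standard error grows by 1/√(1 - ρ²): 1.02 at 0.2 and 1.15 at 0.5. If all three predictors correlate equally at ρ, R² = 2ρ²/(1 + ρ), and the factor is 1.04 at 0.2 and 1.22 at 0.5. For a 5 to 10 year age gap between the sexes alone, the factor on the sex coefficient is 1.01 to 1.04.

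**The case against.** The strongest reply is that this is a descriptive anatomical study. The Aim never promises independent effects, and the crude tests answer the question of where the nerve lies in women, in men, and across age and BMI. If women are older and distance depends on age, the mean distance in women really does differ. A significant gender t-test is then a correct answer to its own hypothesis, so the percentages above are not false-positive rates in the ordinary sense. That stands, and it is why the crude tests should be kept. The percentages apply to the reading that sex or BMI itself matters, which is the reading the Methodology invites.

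Replacing the wording about influence with wording about association would also remove the mismatch. It would do so by narrowing the question, and would still leave open which factor an association belongs to.

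Several smaller points also stand. Every association used is assumed; at the low end the crude rate is 7% against 5%. The distances are small beside 5-10 mm. Masking arises only when the two effects oppose each other; when they act in the same direction, crude power rises. The sentence on Pearson correlation could be read to include age with BMI, which would reveal that one association but not adjust for it. If all three predictors correlate at 0.5, the variance inflation of 1.5 is worth about 200/1.5 = 133 patients, before any gain from lower residual variance.

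**Conclusion.** The concern holds and should be fixed. It is certain from the text that no analysis considers the three factors together and that the design does not balance them. How much this matters in the actual sample depends on the age-sex, age-BMI and sex-BMI associations, which the documents do not give. With none, there is no distortion. With the moderate associations assumed here, a factor with no effect of its own would look significant in roughly 7% to 39% of studies, and a real sex difference of 0.4 SD could be detected as seldom as 25% of the time. The consequence is a wrong statement of which factor matters; the error in distance itself is likely to be about half a millimetre or less.

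**What to change.** Add to the Statistical method one prespecified multiple linear regression of nerve-artery distance on age (continuous, entered once and not also as age group), sex, and BMI (continuous). Report each adjusted coefficient with its 95% confidence interval: mm per 10 years, mm for women versus men, and mm per 5 kg/m². Check the linear age term with a residual plot. Base any statement about which factor is independently associated with nerve position on this model, and describe it as association rather than cause. Keep the Pearson correlations and the age-group and gender t-tests alongside, labelled as unadjusted.

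The cost is one or two sentences and one model fit on variables already in the planned analyses; 200 patients is ample for three predictors. Standard errors rise by the modest factors in step 6 of the working. There is one limit on interpretation: age and sex coefficients adjusted for BMI leave out any effect that acts through BMI, and the report should say so.
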